9.2.4.2 Method of Detecting Adverse Events and Serious Adverse Events

Care will be taken not to introduce bias when detecting adverse events and/or serious adverse events. Open-ended and non-leading verbal questioning of the subject is the preferred method to inquire about adverse event occurrence.

9.2.4.3 Follow-up of Adverse Events and Serious Adverse Events

After the initial adverse event/serious adverse event report, the investigator is required to proactively follow each subject at subsequent visits/contacts. All adverse events and

serious adverse events will be followed until resolution, stabilization, until the event is otherwise explained, or the subject is lost to follow-up (as defined in Section 8.3). Further information on follow-up procedures is given in Section 12.4.

All new information for previously reported serious adverse events must be sent to Amgen within 24 hours following awareness of the new information. If specifically requested, the investigator may need to provide additional follow-up information, such as discharge summaries, medical records, or extracts from the medical records. Information provided about the serious adverse event must be consistent with that recorded on the Events CRF.

9.2.4.4 Regulatory Reporting Requirements for Serious Adverse Events

If subject is permanently withdrawn from protocol-required therapies because of a serious adverse event, this information must be submitted to Amgen.

Prompt notification by the investigator to the sponsor of serious adverse events is essential so that legal obligations and ethical responsibilities towards the safety of subjects and the safety of a study treatment under clinical investigation are met.

The sponsor has a legal responsibility to notify both the local regulatory authority and other regulatory agencies about the safety of a study treatment under clinical investigation. The sponsor will comply with country-specific regulatory requirements relating to safety reporting to the regulatory authority, IRBs/IECs, and investigators.

Individual safety reports must be prepared for suspected unexpected serious adverse reactions according to local regulatory requirements and sponsor policy and forwarded to investigators as necessary.

An investigator who receives an individual safety report describing a serious adverse event or other specific safety information (eg, summary or listing of serious adverse events) from the sponsor will file it along with the IB and will notify the IRB/IEC, if appropriate according to local requirements.

9.2.4.5 Safety Monitoring Plan

Subject safety will be routinely monitored as defined in Amgen's safety surveillance and signal management process.

9.2.4.6 Pregnancy and Lactation

Details of all pregnancies and/or lactation in female subjects and, if indicated, female partners of male subjects will be collected after the start of study treatment and until

30 days after last dose of study drugs for female subjects and 90 days after last dose of study treatment for male subjects.

If a pregnancy is reported, the investigator is to inform Amgen within 24 hours of learning of the pregnancy and/or lactation and is to follow the procedures outlined in Section 12.5. Amgen Global Patient Safety will follow-up with the investigator regarding additional information that may be requested.

Abnormal pregnancy outcomes (eg, spontaneous abortion, fetal death, stillbirth, congenital anomalies, ectopic pregnancy) are considered serious adverse events.

Further details regarding pregnancy and lactation are provided in Section 12.5.

9.2.4.7 Vital Signs

The following measurements must be performed: systolic/diastolic blood pressure, heart rate, temperature, and, if available, respiratory rate and oxygen saturation in the event of a cardiac and/or pulmonary adverse events.

Subject must be in a sitting position in a rested and calm state for at least 5 minutes before blood pressure assessments are conducted. If the subject is unable to be in the sitting position, the subject should be in most recumbent position as possible. The position selected for a subject should be the same that is used throughout the study and documented on the vital signs eCRF. Take 2 blood pressure measurements spaced 1 to 2 minutes apart and additional measurements if the first 2 are more than 10 mmHg apart for either systolic or diastolic blood pressure.

The temperature location selected for a subject should be the same that is used throughout the study and documented on the vital signs eCRF.

9.2.4.8 Electrocardiograms (ECGs)

Subject must be in supine position in a rested and calm state for at least 5 minutes before ECG assessment is conducted. If the subject is unable to be in the supine position, the subject should be in most recumbent position as possible. The ECG must include the following measurements: heart rate, QRS, QT, QTc, and PR intervals. The principal investigator or (eg, designated site physician) will review all ECGs. Once signed, the original ECG tracing will be retained with the subject's source documents. At the request of the sponsor, a copy of the original ECG will be made available to Amgen.

Electrocardiograms will be required in all subjects at screening. Electrocardiogram monitoring is required on cycle 1 day 8 and cycle 2 day 1 at the end of the carfilzomib infusion, and as clinically indicated.

9.2.4.9 Vital Status

Vital status must be obtained for all subjects within the limits of local law. This includes subjects who may have discontinued study visits with or without withdrawing consent and should include interrogation of public databases, if necessary. If deceased, the date and reported cause of death should be obtained.

9.2.4.10 Other Safety

9.2.4.10.1 Echocardiogram

All subjects will have a baseline complete ECHO, not simply clearance of left ventricular ejection fraction (LVEF), including assessments of systolic and diastolic left ventricular function and right ventricular function and valvular stenosis or insufficiency. Screening ECHO may be done within 28 days prior to enrollment, if performed as a part of standard of care. Echocardiogram is to be repeated approximately every 6 months (± 2 weeks) from cycle 1 day 1 until safety follow-up visit, or more often if clinically indicated. An ECHO must be performed within 72 hours of the onset of a suspected cardiac failure event. Real-time blood pressure at time of ECHO will be collected on the CRF.

9.2.4.10.2 Pulmonary Function Tests (PFTs)

Pulmonary function tests include spirometry to measure FEV1, %FEV1, FEV1/forced vital capacity, forced vital capacity, and diffusing capacity of the lungs for carbon monoxide (DLCO) assessment. Screening PFT measurements may be done within 28 days prior to enrollment, if performed as a part of standard of care. All subjects will have PFTs assessed approximately every 6 months (± 2 weeks) from cycle 1 day 1, until safety follow-up visit, or more often if clinically indicated. Serial measurements should be performed with the same equipment and comparable procedure.

9.2.4.10.3 Hepatitis B

All hepatitis testing will be performed locally. All subjects will be tested at screening for HBsAg, anti-HBs, and anti-HBc, unless performed within 6 months of screening and there was no change in the subject's risk factors within these 6 months.

Subjects with no history of HBV infection that are negative for hepatitis serologies at screening should be followed as clinically indicated.

Subjects with positive testing or who have a prior history of HBV infection should have consultation with a specialist in HBV and have HBV DNA testing and monitoring of HBV DNA every 12 weeks (\pm 2 weeks) through safety follow-up. Subjects that have received Hepatitis B vaccination with only anti-HBs positivity and no clinical signs of hepatitis do not require HBV DNA monitoring.

Any subject who becomes HBV DNA positive or develops reactivation of HBV will have study treatment interrupted and receive appropriate anti-viral treatment and prophylaxis as per institutional guidelines. Resumption of clinical study therapy may be considered in subjects whose HBV reactivation is controlled and where the benefits of clinical study therapy outweigh the risks. After cessation of study therapy for any reason, any ongoing monitoring and anti-viral treatment should be under the guidance of a specialist in HBV.

9.2.5 Clinical Laboratory Assessments

Refer to [12.2](#) for the list of clinical laboratory tests to be performed and to the Schedule of Activities ([Table 2-1](#)) for the timing and frequency.

The investigator is responsible for reviewing laboratory test results and recording any clinically relevant changes occurring during the study in the Events CRF. The investigator must determine whether an abnormal value in an individual study subject represents a clinically significant change from the subject's baseline values. In general, abnormal laboratory findings without clinical significance (based on the investigator's judgment) are not to be recorded as adverse events. However, laboratory value changes that require treatment or adjustment in current therapy are considered adverse events. Where applicable, clinical sequelae (not the laboratory abnormality) are to be recorded as the adverse event.

All protocol-required laboratory assessments, as defined in Section [12.2](#), must be conducted in accordance with the laboratory manual and the Schedule of Activities ([Table 2-1](#)).

9.2.5.1 Pregnancy Testing

A high sensitive (urine or serum) pregnancy test should be completed 14 days prior to first dose of study drug and again 24 hours prior to first dose of study drug for females of childbearing potential.

Note: Females who have undergone a bilateral tubal ligation/occlusion should have pregnancy testing per protocol requirements. If a female subject, or the partner of a

male subject, becomes pregnant it must be reported on the Pregnancy Notification Worksheet, see [Figure 12-2](#). Refer to Section [12.5](#) for contraceptive requirements.

Additional pregnancy testing must be performed weekly during the first 4 weeks of pomalidomide use followed by a pregnancy test every 4 weeks in females with regular menses or every 2 weeks in females with irregular menstrual cycle, and approximately 30 days after the last dose of study drugs.

Additional on-treatment pregnancy testing may be performed at the investigator's discretion or as required per local laws and regulations.

9.2.6 Pharmacokinetic Assessments

Approximately 20 subjects will be invited to participate in an optional pharmacokinetic (PK) substudy.

Venous samples of approximately 2.5 mL will be collected for measurement of plasma concentrations of carfilzomib as specified in the Schedule of Activities ([Table 2-1](#)).

Instructions for the collection and handling of biological samples will be provided by the sponsor. The actual date and time (24-hour clock time) of each sample will be recorded.

Samples will be collected within \pm 5-minute time windows around the nominal time points (except for the time point immediately prior to the end of infusion, for which the PK collection needs to occur prior to the end of infusion).

9.2.7 Pharmacodynamic Assessments

Approximately 20 subjects will be invited to participate in an optional PDn substudy.

Venous blood samples of approximately 6 mL will be collected for measurement of proteasome inhibition as specified in the Schedule of Activities ([Table 2-1](#)).

9.2.8 Pharmacogenetic Assessments

If the subject consents to the optional pharmacogenetics portion of this study, bone marrow aspirate (1 – 2 mL in EDTA) will be collected and sent to the central laboratory for CD138 selection of tumor cells. The bone marrow samples will be collected from consenting subjects during screening and at disease progression if a bone marrow biopsy is performed to confirm. These optional pharmacogenetics analyses focus on inherited genetic variations to evaluate their possible correlation to the disease and/or responsiveness to the therapies used in this study. The goals of the optional studies include the use of genetic markers to help the investigation of and/or to identify subjects who may have positive or negative response to the therapies administered in this study.

9.2.9 Biomarker Samples

If the subject consents to the optional biomarker portion of this study, 2 to 5 mL of peripheral blood in EDTA will be collected at screening and at the time of bone marrow evaluation for determination of MRD. Samples will be frozen and stored for later use in exploring methods for MRD detection of [REDACTED] in peripheral blood. The levels of [REDACTED] will be compared to results from screening peripheral blood and MRD measurements in the bone marrow from the 12- and 24-month assessments \pm 4 weeks.

10. Statistical Considerations

10.1 Sample Size Determination

The sample size was determined based on feasibility and the intent to optimize the power for testing the primary hypothesis at 1-sided alpha of 0.05. With 85 subjects, the power for testing the primary hypothesis and secondary hypothesis at 1-sided alpha of 0.05 is expected to be more than 85%. As these estimates are based on recent data available in the study population (eg, sub-populations within clinical trials CANDOR and A.R.R.O.W.), additional scenarios, **including those based on the actual number of subjects who received at least one dose of carfilzomib (52 subjects)**, for the experimental arm and power are included in [Table 10-1](#).

Table 10-1. Power and Hypothesized Treatment Effect

Hypothesis	Sample Size	H0	H1	Power
Primary	85	ORR \leq 60%	ORR \geq 75%	90.4%
	85	ORR \leq 60%	ORR \geq 80%	99.3%
	52	ORR \leq 60%	ORR \geq 75%	69.2%
	52	ORR \leq 60%	ORR \geq 80%	91.8%
Secondary	85	MRD[-]CR rate at 12 months \leq 3%	MRD[-]CR rate at 12 months \geq 10%	86.4%
	85	MRD[-]CR rate at 12 months \leq 3%	MRD[-]CR rate at 12 months \geq 12%	95.1%
	52	MRD[-]CR rate at 12 months \leq 3%	MRD[-]CR rate at 12 months \geq 10%	60.5%
	52	MRD[-]CR rate at 12 months \leq 3%	MRD[-]CR rate at 12 months \geq 12%	76.3%

MRD[-]CR = minimal residual disease negative complete response; ORR = overall response rate

10.2 Analysis Sets, Subgroups, and Covariates

10.2.1 Analysis Sets

Safety Analysis Set

The Safety Analysis Set includes all enrolled subjects who received at least 1 dose of carfilzomib. The analysis of efficacy and safety analyses will be based on the Safety Analysis Set.

MRD Evaluable Analysis Set

The MRD Evaluable Analysis Set includes all enrolled subjects with measurable MRD status at baseline and at least 1 measurable MRD status post baseline (subjects who don't have measurable MRD status due to technical issues will be excluded), who received at least 1 dose of carfilzomib. The MRD sensitivity analysis will be based on MRD Evaluable Analysis Set.

Pharmacokinetic Analysis Set

The PK Analysis Set will include a subset of up to 20 evaluable subjects in Safety Analysis Set, who have participated in the PK assessment. Evaluable subjects are defined as those subjects providing sufficient PK samples to permit estimation of PK parameters on cycle 2 day 1.

10.2.2 Covariates

The relationship of covariates to efficacy endpoints will be explored if appropriate.

10.2.3 Subgroups

Primary endpoints will be examined for the below subgroup analysis, if appropriate:

- prior carfilzomib exposure (yes vs no)
- number of prior lines of therapy (1 vs 2)
- timing of lenalidomide refractoriness (during maintenance: yes vs no)

10.2.4 Handling of Missing and Incomplete Data

Subjects may have missing data points for various reasons and the impact on the analysis might differ from 1 endpoint to another. The general rules for accommodating the missing or incomplete data may be refined during the review of the data, and they will be described in detail in the statistical analysis plan (SAP). Sensitivity analyses might be needed to evaluate the robustness of the primary analysis results in case of significant missing data. Incomplete dates for the start of adverse event, concomitant medications, and death will be imputed and the detailed rules will be specified in the SAP.

10.3 Adaptive Design

Adaptive design is not applicable for this study.

10.4 Statistical Analyses

The SAP will be developed and finalized before database lock. Below is a summary of the timing and methods for the planned statistical analyses. To preserve study integrity, the final analysis will be conducted and reported following the end of study, as defined in Section 5.3.1.

10.4.1 Planned Analyses

10.4.1.1 Primary Analysis

The primary analysis will be triggered **12 months after the last subject enrollment**.

The primary analysis will be based on a clean database lock.

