Protocol Title: An Open-label, Phase 2 Study Treating Subjects with First or Second Relapse of Multiple Myeloma with Carfilzomib, Pomalidomide, and Dexamethasone (KPd)

Short Protocol Title: A Study Evaluating Treatment of Multiple Myeloma with Carfilzomib in Combination with Pomalidomide and Dexamethasone

Study Phase: 2

Indication: Relapsed multiple myeloma

Rationale:

This trial is designed to estimate the efficacy of a carfilzomib-based triplet in first or second relapse of multiple myeloma for subjects refractory to lenalidomide.

Objective(s)/Endpoint(s)

Objectives	Endpoints
Primary	

 Estimate the overall response rate (ORR) 	
 objective response defined as the best overall confirmed response of partial response (PR), very good partial response (VGPR), complete response (CR), or stringent complete response (sCR) by Independent Review Committee (IRC) per International Myeloma Working Group Uniform Response Criteria (IMWG-URC)
Key Secondary	

 Estimate the rate of minimal residual disease negative complete response (MRD[-]CR) at 12 months landmark 	
 MRD[-]CR at a sensitivity of 10^{-5} using next generation sequencing (NGS)-based method in the bone marrow at 12 months \pm 4 weeks from start of treatment
Secondary	

 Describe the safety and tolerability of carfilzomib combined with dexamethasone and pomalidomide 	
 subject incidence of treatment-emergent adverse events

 Estimate the frequency of best MRD[-] response in KPd 	
 MRD[-] response at a sensitivity of 10^{-5} using NGS-based method in the bone marrow at any time during therapy

 Estimate the frequency of sustained MRD[-]CR 	
 sustained MRD[-]CR at a sensitivity of 10^{-5} using NGS-based method in the bone marrow defined as subjects that maintain MRD[-]CR 12 months or more after achieving MRD[-]CR status, disregarding when the first MRD[-]CR was reached

Objectives	Endpoints

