10.4.2.2 Efficacy Analyses

Endpoint	Statistical Analysis Methods
Primary	
Overall Response Rate
 
Overall Response Rate (ORR) is defined as the proportion of subjects that reach the overall response among all subjects who received at least 1 dose of the carfilzomib.
 
It will be calculated along with the associated 90% and 95% exact binomial CIs that will be estimated using the Clopper-Pearson method. The lower bound of the 90% exact binomial CI is evaluated whether it is larger than the reference ORR. If that happens, then the primary objective is met.

Key Secondary	
MRD[-]ICR at 12 months at a sensitivity of 10⁻⁵ using NGS-based method in the bone marrow
 
MRD[-]ICR rate at 12 months landmark is defined as the proportion of subjects who reach MRD[-]ICR at 12 months landmark assessment among all subjects who received at least 1 dose of carfilzomib.
 
The rate will be calculated along with the associated 90% and 95% exact binomial CIs that will be estimated using the Clopper-Pearson method. If the primary objective is met, then the lower bound of the 90% exact binomial CI is evaluated whether it is greater than the reference MRD[-]ICR rate. If that happens, the key secondary objective is met.
 
The primary analyses for the key secondary endpoint will be based on the safety analysis set, while the sensitivity analyses will be performed on the MRD-evaluable analysis set.
 
The data for the key secondary endpoint will include the MRD results from bone marrow samples obtained from subjects with suspected CR or better obtained no earlier than 8 months and no later than 12 months (+ 4 weeks) after enrollment.

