	
period of maintaining MRD[-]CR can have a window of ± 4 weeks, ie maintaining MRD[-]CR for at least 12 months (- 4 weeks) is considered as sustained.
 
Sustained MRD[-]CR at 24 months ± 4 weeks
 
Sustained MRD[-]CR rate at 24 months ± 4 weeks is defined as the proportion of subjects that maintain MRD[-]CR for 12 months or more after achieving MRD[-]CR status at their first MRD assessment at 12 months landmark.
 
It will be calculated along with the associated 90% and 95% exact binomial CIs that will be estimated using the Clopper-Pearson method. The 12 month period of maintaining MRD[-]CR can have a window of ± 4 weeks, ie, maintaining MRD[-]CR for at least 12 months (- 4 weeks) is considered as sustained.
 
Duration of Response (DOR)
 
Duration of response will be calculated for subjects who achieve sCR, CR, VGPR, or PR from the first date of PR or better to the date of disease progression or death due to any cause. If a subject is alive or lost to follow-up without experiencing documented disease progression by the data cutoff date, the DOR for the subject will be censored at the date of last valid disease and response assessment. The distribution of DOR including the median will be characterized using the Kaplan-Meier method based on the subjects who achieve best overall response of sCR, CR, VGPR or PR.
 
Time to Response
 
Time to response will be summarized with the non-missing sample size (n), mean, standard deviation, median, minimum, and maximum for responders, ie, subjects who achieve best overall response of sCR, CR, VGPR, or PR.
 
Progression Free Survival (PFS)
 
Progression Free Survival will be calculated from the time of start of treatment until disease progression or death due to any cause, whichever occurs first. If a subject is alive or lost to follow-up without experiencing documented disease progression by the data cutoff date, the PFS data for the subject will be censored at the date of last valid disease and response assessment. Detailed PFS data censoring rule will be described in the SAP. The distribution of PFS, including median, will be estimated using the Kaplan-Meier method. PFS rate at the selected time points (12 months and 24 months) will be reported. The 90% and 95% CIs for the median and other percentiles of PFS will be constructed using the method of Klein and Moeschberger (1997) with log-log transformation. The 90% and 95% CIs for PFS rates will be estimated using the methods by Kalbfleisch and Prentice (1980) with log-log transformation.
 
Overall Survival (OS)
 
Overall survival will be calculated from date of start of treatment until death due to any cause. Subjects still alive will be censored at the date last known to be alive.
 
OS will be analyzed using the same method as described for the PFS endpoints.
 
Complete Response or better rate (CR)
 
The CR will be analyzed using the same methods as described for ORR.

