- **Date Decision Was Made to End Investigational Product on End of Investigational Product Administration (Carfilzomib), Date Decision Was Made to End Non-Investigational Product on End of Non-Investigational, Product Administration (Dexamethasone), End of Investigational Product Administration (Pomalidomide) and End of Non-Investigational Product Administration (Pomalidomide) CRFs, where the Primary Reason for ending treatment is not Death or Lost to follow-up**

MRD[-]ICR

MRD[-]ICR is defined as achievement of CR (including sCR) per IMWG-URC and MRD[-] status at a sensitivity of 10^{-5} using next generation sequencing (NGS) based method in the bone marrow at any time.

MRD[-]ICR Rate at 12 Months Landmark

MRD[-]CR rate at 12 months landmark is defined as proportion of subjects who reach MRD[-]CR at 12 months landmark assessment among all subjects who received at least 1 dose of carfilzomib. **The sensitivity analysis of MRD[-]CR Rate at 12 months landmark will be based on MRD Evaluable Analysis Set.** The data will include the MRD results from bone marrow samples obtained from subjects with Suspected CR or better obtained no earlier than 8 months and no later than 12 months plus 4 weeks after the start of any study treatment.

MRD[-] Rate at Any Time During Therapy

MRD[-] rate at any time during therapy is defined as proportion of subjects who reach MRD[-] at any time during therapy among all subjects who received at least 1 dose of carfilzomib. **The sensitivity analysis of MRD[-]CR Rate at any time during therapy will be based on MRD Evaluable Analysis Set.** The data will include the MRD results from bone marrow samples obtained from the subjects with a response of VGPR or better at any time during therapy.

Number of cycles started for any study drug

It is defined as the total number of treatment cycles in which at least one dose of any study drug is administered.

Number of cycles started for each study drug

It is defined as the total number of treatment cycles in which at least one dose of carfilzomib/pomalidomide/dexamethasone, respectively, is administered.

Number of cycles started for all study drugs

It is defined as the total number of treatment cycles in which at least one dose of carfilzomib, one dose of pomalidomide and one dose of dexamethasone is administered.

Number of doses of carfilzomib administered

It is defined as the total number of non-zero doses of carfilzomib a subject received during the treatment period of the study

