
Number of doses of pomalidomide administered

It is defined as the total number of non-zero doses of pomalidomide a subject received during the treatment period of the study

Number of doses of dexamethasone administered

It is defined as the total number of non-zero doses of dexamethasone a subject received during the treatment period of the study

Overall Response (OR)

OR is the best overall confirmed response of partial response (PR), very good partial response (VGPR), complete response (CR), or stringent complete response (sCR).

Overall Response Rate (ORR)

Overall Response Rate (ORR) is defined as the proportion of subjects that reach the overall response among all subjects who received at least 1 dose of the carfilzomib.

Overall Survival (OS)

OS is defined as time from start of treatment until death from any cause.

$OS = (\text{Death date or date of censoring if censored} - \text{start of any study treatment date} + 1) / 30.4$

Subjects still alive will be censored at the date last known to be alive. If the date last known to be alive is after the date that triggers the analysis (ie, the data cutoff date), the subject will be censored at the analysis trigger date.

Progression Free Survival (PFS)

PFS is defined as the time from the first dose date of any study treatment until the first documentation of disease progression or death due to any cause, whichever occurs first in the absence of subsequent anticancer therapy and if not > 70 days from the last non-NE, post-baseline disease assessment. PFS will be censored at the last non-NE, post-baseline disease assessment or the earlier of the following, where applicable: (a) the last non-NE, post-baseline disease assessment prior to subsequent anticancer therapy, or (b) the last non-NE, post-baseline assessment followed > 70 days later by disease progression or death; otherwise, at first dose date. Disease progression is based on the IMWG-URC [2016].

PFS time in months= [(PD or death date, whichever occurs first) or date of censoring if censored– start of treatment date + 1] / 30.4.

Table 5-1. Conventions for Censoring for PFS

Situation	Date of Progression or Censoring	Outcome
No PD or death, no new anticancer treatment	Last visit; otherwise, first dose date of any study treatment	Censored
No PD or death, new anticancer treatment	Last visit prior to new treatment; otherwise, first dose date of any study treatment	Censored

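### The only cutoff the documents define, the primary-analysis trigger, falls 28 to 31 days before the key secondary MRD[-]CR sampling window closes for the last enrolled subject

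*Protocol*

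**What the plan says.** **Trigger.** Protocol 10.4.1.1 and SAP 7.1 both start the primary analysis "12 months after the last subject enrollment". The protocol adds: "The primary analysis will be based on a clean database lock". SAP 7.1 says the same. Neither section gives a lock date or a last date for MRD samples.

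**Cutoff.** SAP Section 5, in the overall survival definition, has a rule that begins "If the date last known to be alive is after the date that triggers the analysis (ie, the data cutoff date" and then censors survival at the trigger date. This is the only place where either document says what the cutoff date is. Protocol 10.4.2.2 censors DOR and PFS for subjects "without experiencing documented disease progression by the data cutoff date", but does not define that date.

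**Sampling window.** For the key secondary test, Protocol 10.4.2.2 states: "The data for the key secondary endpoint will include the MRD results from bone marrow samples", taken from subjects with suspected CR or better and "obtained no earlier than 8 months and no later than 12 months (+ 4 weeks) after enrollment". SAP Section 5 opens the window at 8 months too, and closes it "no later than 12 months plus 4 weeks after the start of any study treatment". The endpoint itself, in the Protocol Synopsis and Protocol 4.1, is timed at 12 months ± "4 weeks from start of treatment". The denominator is every subject who received carfilzomib.

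**Other analyses.** Protocol 10.4.1.2 and 10.4.1.3 (SAP 7.2 and 7.4) make the sustained-MRD and final analyses wait until all subjects could have completed the relevant assessment or visit. The primary analysis has no such condition.

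**The concern.** The key secondary hypothesis is formally tested at the primary analysis, after ORR in a fixed sequence. Its data rule admits samples for four weeks beyond the 12-month point, but the analysis is triggered at 12 months from last enrolment. If the SAP's equation of trigger and cutoff is applied to MRD, a late enrollee with a suspected CR whose marrow is taken after the trigger, but inside the window, is left out of the numerator and kept in the denominator. That would conflict with the endpoint's own data rule, and the result would depend on a cutoff choice settled only at lock.

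The test turns on very few events, so even one lost responder could matter. The stakes are still limited: the loss runs in one direction, towards a lower rate and lower power.

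**Working it through.** **1. Reproduce the plan's power.** Inputs from Protocol Table 10-1 and SAP Table 3-1: n = 52, reference rate 3%, true rate 12% or 10%, lower limit of the two-sided 90% Clopper-Pearson interval.

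- Lower limit for x events = 5th percentile of Beta(x, 52 − x + 1). For x = 4 it is 2.67%; for x = 5 it is 3.87%. The test therefore needs 5 events.
- P(X ≥ 5 | 52, 0.12) = 76.3% and P(X ≥ 5 | 52, 0.10) = 60.5%. Both match the plan.
- Exact one-sided alpha: P(X ≥ 5 | 52, 0.03) = 0.0196.

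**2. Gap between trigger and window close.** Let E be the last enrolment date and L the lag to first dose, 0 to 3 days (Protocol 9.1.2).

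- Trigger = E + 12 months.
- Close, enrolment anchor = E + 12 months + 28 days. Gap = 28 days.
- Close, treatment-start anchor = E + L + 12 months + 28 days. Gap = 28 + L = 28 to 31 days.

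This assumes that the last enrollee was dosed; 52 of 54 enrolled subjects were. A subject enrolled d days earlier has a gap shorter by d days, so only those enrolled in about the last 4 weeks of accrual are exposed.

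**3. Share of the window after the trigger, for the last enrollee.** The window runs from month 8 (about day 243) to 12 months + 4 weeks (day 393), which is 150 days. Remaining: 28/150 = 18.7% to 31/150 = 20.7%. If a subject is sampled only in the scheduled ± 4 weeks (56 days), the share is 28/56 = 50% to 31/56 = 55%.

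**4. Illustrative power.** Assumptions not in the documents:

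- k late enrollees lose a fraction s of their samples, and a lost sample counts as not MRD[-]CR. That handling is inferred from the all-dosed denominator and SAP 8.3, which imputes no missing outcomes.
- Accrual of 18 to 24 months would give 54/(18 × 30.4/28) = 2.8 to 54/(24 × 30.4/28) = 2.1 subjects per 4 weeks, hence k = 1 to 3.

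The number of events is Binomial(52 − k, p) + Binomial(k, p(1 − s)), with at least 5 required:

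| k | s | Power at 12% | Power at 10% |
|---|---|---|---|
| 0 | – | 76.3% | 60.5% |
| 1 | 0.2 | 76.0% | 60.1% |
| 3 | 0.2 | 75.4% | 59.4% |
| 6 | 0.5 | 71.5% | 55.0% |
| 1 | 1 | 74.8% | 58.7% |
| 3 | 1 | 71.5% | 55.0% |

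Expected events lost at 12% with s = 0.2 are k × 0.12 × 0.2: 0.024 for k = 1 and 0.072 for k = 3. Alpha at 3% falls from 0.0196 to 0.0188 (k = 3, s = 0.2) or 0.0156 (k = 6, s = 0.5). It never rises.

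**5. Anchor.** Protocol 10.4.2.2 counts from enrolment. The Synopsis, Protocol 4.1 and SAP Section 5 count from start of treatment. The difference is at most 3 days, or 3/150 = 2% of the window.

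**The case against.** The strongest reply is that nothing need be lost. A trigger followed by a clean lock does not say that data stop at the trigger. The SAP's survival rule exists because contact dates after the trigger are expected in the database; it truncates survival explicitly, and no such truncation is written for MRD. The endpoint's own rule admits samples to 12 months plus 4 weeks, and a rule specific to an endpoint would ordinarily prevail over a term explained inside another endpoint's censoring rule. This reading is reasonable, but it is inferred. The plan does not choose between the two, and even the no-loss reading needs a lock later than the last window, which is not stated either.

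It is also fair that exposure is small. Only subjects with suspected CR or better are sampled, and a sample from month 8 onward can replace the 12-month one (Protocol 5.1 and 9.2.2.2). Recruitment stopped amid enrolment difficulties, so average accrual may not describe the last four weeks. The last enrollee may not have been dosed. All of this stands.

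A reader might go further and infer that no data cutoff is stated at all. The survival rule in the SAP does state one; what is missing is whether it governs MRD. A reader might also infer that samples will be lost, or that the primary result is at risk. The first holds only if the trigger is applied as the MRD cutoff, and nothing here touches ORR.

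**Conclusion.** The point holds as a minor one. The only defined cutoff precedes the close of the key secondary window by 28 to 31 days for a dosed last enrollee, and no text says whether later in-window samples count.

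The date arithmetic and the 5-of-52 rule are firm. The consequence is conditional on the trigger serving as the MRD cutoff. Its size is illustrative: 0.3 to 0.9 points of power at a true 12% and 0.4 to 1.1 points at 10%, for one to three late enrollees each losing 20% of samples. Complete loss would cost more, 1.5 points for one subject at 12%. The direction is always conservative.

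The enrolment anchor would not merit a comment alone, since the SAP already uses start of treatment.

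**What to change.** In Protocol 10.4.1.1 and SAP 7.1, adopt one of two sentences:

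- **Move the cutoff.** Set the primary-analysis cutoff at the point when all treated subjects could have completed the 12-month plus 4-week MRD assessment, which is at most 12 months + 31 days after last enrolment. The model wording is in Protocol 10.4.1.2. The cost is about 4 weeks' delay.
- **Keep the trigger.** State that every sample within the SAP Section 5 window counts at the primary database lock, and that the lock follows the close of the last treated subject's window. The cost is one sentence in each document and a constraint on the lock date.

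Neither option needs separate cutoffs for ORR and MRD[-]CR. As an accompanying editorial correction, change the anchor in the key secondary row of Protocol 10.4.2.2 from enrolment to start of treatment.
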